Sample size. Most RADTs are very specific⁹. Sensitivity is the limiting factor, and the sensitivity from better performing previous studies is in the range of 80-90%.⁹ However we will be comparing a rapid test versus the results from the same throat swab which should provide higher sensitivities. Assuming 25% of the sample have streptococcus (based on our piloting) and a sensitivity of 85%-95% for the best RADT to estimate, with 95% confidence, sensitivity to within +/-5% (i.e. to be confident that the sensitivity is not less than 80% which would be less useful clinically) then 73 to 196 samples with streptococcus are required for each RADT (see table below), or 292-784 in total, 1460- 3920 allowing for the 5 RADTs, or 1500-4000 allowing for some leeway in the assumptions. If each adult provides four comparisons and each child two, then 400-1200 patients are required. Thus our minimum sample size is 438 and maximum 1176.

Sample size to estimate sensitivity with 95% confidence intervals of +/-5%

	Sensitivity		
	85%	90%	95%
Sample with streptococcus present	196	139	73
Sample for each RADT	784	556	292
(assuming 25% have streptococcus)			
Total number of tests (for 5 RADTs)	3920	2780	1460
Number of patients required (assuming two	1176	834	438
double swabs in adults and one double swab in			
children)			

²⁾ Clinical rule and clinical outcomes.

• Development of Clinical rule.

Confirming the validity of the Centor criteria in a modern UK primary care population. This study provides an opportunity to modify a clinical rule (such as Centor) which aims to predict the results of throat swabs. The rationale for this is that there have been no UK studies which have independently predicted the presence of Streptococcus (the Dobbs score used univariate analysis only, hence was over inclusive and rather unwieldy⁶); furthermore multivariate analysis of our pilot data in 120 individuals suggest the key independent variables to predict the presence of streptococcus were a history of fever at any time in the illness, a history of fever in the last 24 hours, the absence of cough, anterior cervical glands and muscle aches i.e. different from Centor. There are no additional costs to this aspect of the study since we will be documenting clinical details and taking throat swabs anyway

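### The Phase I sample sizes give the stated +/-5-point precision, but not the stated confidence that sensitivity is at least 80% when true sensitivity is 85%

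*Protocol*

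**What the plan says.** In the Protocol, Methods: Phase 1, 1) Clinical study of RADTs, the Sample size paragraph assumes "a sensitivity of 85%-95% for the best RADT to estimate, with 95% confidence, sensitivity to within +/-5" percentage points. A bracket introduced by *i.e.* then gives the meaning of that precision: "to be confident that the sensitivity is not less than 80% which would be less useful clinically". The result is stated as "then 73 to 196 samples with streptococcus are required for each RADT". The table below the paragraph gives 196, 139 and 73 positives at sensitivities of 85%, 90% and 95%, under the heading "Sample size to estimate sensitivity with 95% confidence intervals of +/-5" per cent. The same paragraph says of earlier work that "the sensitivity from better performing previous studies is in the range of 80-90" per cent, and expects higher values here because test and culture use the same swab. It states no power, and no probability that a confidence limit will clear 80%.

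**The concern.** A half-width of 5 points fixes how wide the interval is expected to be. It does not fix where the interval will fall. The 80% floor is 85% minus 5 points; the other two columns minus 5 points give 85% and 90%. The bracket therefore belongs to the 85% column. In that column, 196 is the number at which an observed sensitivity of 85% has a lower limit at 80%. If 85% is the true value, the observed value falls below it roughly half the time, and the lower limit then falls below 80%.

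At stake is what a reader will believe Phase I can show. The Protocol itself regards sensitivity under 80% as less useful in practice, and Phase I supplies the test carried into the Phase II trial. A reader of the Sample size paragraph would expect Phase I to establish that a test with 85% sensitivity clears 80%.

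**Working it through.** **Inputs** (all from the Sample size paragraph and its table): two-sided 95% confidence, z = 1.96; half-width d = 0.05; assumed sensitivity p = 0.85, 0.90 or 0.95; floor 0.80; prevalence of streptococcus 25%; five tests.

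**1. The plan's own figures.** n = z²p(1−p)/d², rounded up.
- p = 0.85: 3.8416 × 0.1275 / 0.0025 = 195.9, so 196.
- p = 0.90: 3.8416 × 0.0900 / 0.0025 = 138.3, so 139.
- p = 0.95: 3.8416 × 0.0475 / 0.0025 = 73.0, so 73.

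Dividing by 0.25 gives 784, 556 and 292 samples per test. Multiplying by 5 gives 3920, 2780 and 1460 tests. All agree with the table.

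**2. What counts as a lower limit of at least 80%.** For each n, find the smallest number r of test-positive results among the streptococcus-positive samples whose two-sided 95% lower limit is at least 0.80. For n = 196:
- Wald: r = 167 (observed 85.2%).
- Wilson and Clopper-Pearson (exact): r = 168 (observed 85.7%).

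**3. Chance of reaching r.** This is the binomial tail P(X ≥ r) with X ~ Bin(n, p). In each row of the table below, p is the true sensitivity.

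| Positives n | True sensitivity | r, Wald | Chance, Wald | r, Wilson and exact | Chance, Wilson and exact |
|---|---|---|---|---|---|
| 196 | 85% | 167 | 51.7% | 168 | 43.8% |
| 139 | 90% | 120 | 93.8% | 121 | 90.0% |
| 73 | 95% | 64 | 99.7% | 66 | 97.1% |
| 139 | 85% | 120 | 38.4% | 121 | 29.5% |
| 73 | 85% | 64 | 32.8% | 66 | 12.6% |

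As a cross-check of the first row, the normal approximation gives Φ(0.05/√(0.1275/196) − 1.96) = Φ(0.00) = 50%.

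**4. Sensitivity to the choices made.** With a one-sided 95% bound, 196 positives at true 85% give 51.7-59.6% across the same methods. With 196 positives and a two-sided limit, the chance rises with the true value (Wald, then Wilson and exact): 81% and 74% at 87%, 90% and 86% at 88%, 99% and 98% at 90%.

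**The case against.** The strongest defence is that the plan makes a precision statement and nothing more. On that view the bracket says only that an interval centred on an estimate of 85% runs down to 80%, which is true. That explains the wording but does not rescue it. In the sentence, 85% is an assumption about the test, not an observed result, and confidence about 80% is given as the meaning of the sample size.

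A second defence is that 85% is the least favourable value in the range, and that the plan expects better from same-swab comparison. This stands in part: the bracket is sound at 90% and 95%, and with 196 positives it becomes reasonable from about 88%. But 85% is an explicit planning value, and it is the one that sets the maximum sample of 1176 patients.

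Two stronger readings should be resisted.
- A reader might infer that a test with 85% sensitivity would fail Phase I selection about half the time. The documents do not support this. The criterion of more than 80%, in the Analysis section, is applied to previous studies when choosing which kits to evaluate. No passage drops a kit because its Phase I lower limit is below 80%; Phase II takes the best performer.
- A reader might infer that the table is wrong or the study too small. The table reproduces in full, and the plan sets no Phase I power target that it misses.

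**Conclusion.** The point holds as a correction of a stated assurance. The sample sizes deliver the +/-5-point precision. They do not deliver confidence that sensitivity is at least 80% across the assumed range. At true 85% with 196 positives, the chance of a two-sided 95% lower limit at or above 80% is about 44-52%. If the achieved number of positives matches a smaller column while the truth is 85%, the chance is lower still.

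The conclusion does not depend on the interval method or on using a one-sided bound. It assumes that the positive samples for a given test are independent and that the number of positives equals the planned figure. The severity is minor to moderate: no Phase I decision rule in the Protocol depends on the 80% limit.

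**What to change.** In the Phase I Sample size paragraph, state that the numbers give a 95% confidence interval of about +/-5 points. Either delete the bracket about 80%, or limit it to a true sensitivity of about 90% or more. Add one sentence with the figures: with the tabulated numbers, the lower limit is at least 80% with probability of about 90-94% at true 90% and 97% or more at true 95%, but only about 44-52% at true 85%. Name the interval method used.

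The cost is one or two sentences and a less favourable stated assurance. The table, the analysis and the patient numbers stay as they are.

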These clinical outcomes will provide information to confirm the sample size calculation for the phase 2 trial, and will allow exploration of the predictive value of throat swabs/rapid tests and clinical data for symptom resolution and reconsultation/complications.

3) In vitro study of RADTs.

The number of organisms harvested crucially determine the performance of the RADT¹², and two well taken samples from the same individual will predict the other results with a sensitivity of 83%-91%.¹⁴⁻¹⁶ Variation in RADT performance eliminating sampling bias will be assessed by in parallel in vitro studies (using different antigen loads comparable to the data coming from clinical studies, and also controls). The most recent and comprehensive of in vitro studies compared 16 tests but only included 4 of the 5 tests proposed¹⁷, and performed very few tests for each RADT. Thus more comprehensive comparative data is needed. As in the most recent in vitro study¹⁷we will compare the performance of RADTs using 4 strains of group A

As in the most recent in vitro study we will compare the performance of RADTs using 4 strains of group A beta haemolytic streptococci and a control strain (a group C streptococcus, or Moraxella), in three dilutions each $(10^5, 10^6, \text{ and } 10^7 \text{ Colony forming units per ml})$ corresponding to the range of growths normally seen from throat swabs in the community. We will perform 20 tests for each RADT at each dilution and for each strain (i.e. 200 tests for each RADT) which will provide similar power to the clinical study.

Assessing ease of use of RADTs by clinicians.

Most of the in vitro tests will be carried out by laboratory personnel who will rate ease of use, but we will also arrange a panel of 10 GPs and practice nurses - who will perform the tests in clinical practice – to perform four tests with each RADT, and the order of RADTs will be randomised. Several tests are required so that each clinician gets used to doing each test competently. For each test the clinician will document time to do the test, time to get the result (seconds), overall ease of use (on a five point Likert scale – very easy, easy, neither easy nor difficult, difficult, very difficult) and clarity of result (clear, unclear). After using all the RADTs each clinician will be asked to rank the RADTs in order of their overall preference.

4) Qualitative study.

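### The in vitro study's stated total of 200 tests per RADT contradicts its own factors, which multiply to 300

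*Protocol*

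**What the plan says.** The design is set out in the Protocol, Methods: Phase 1, 3) In vitro study of RADTs. The material is "4 strains of group A beta haemolytic streptococci and a control strain (a group C streptococcus, or Moraxella), in three dilutions each", and the three concentrations are listed as 10^5, 10^6 and 10^7 colony forming units per ml. The next sentence gives replication and total together: "We will perform 20 tests for each RADT at each dilution and for each strain (i.e. 200 tests for each RADT"). The same sentence then attaches a claim about power to that total: "which will provide similar power to the clinical study".

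The comparator is in 1) Clinical study of RADTs, Sample size. There, each RADT needs 196, 139 or 73 streptococcus-positive samples to estimate a sensitivity of 85%, 90% or 95% to within 5 percentage points with 95% confidence. Five RADTs are planned.

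**The concern.** The total is introduced as the product of the factors before it, and it is not their product. The two statements describe experiments of different size. A laboratory that follows the per-cell instruction runs half as many tests again as the stated total. A laboratory that works to the total has to drop a dilution, drop strains or cut replicates, and the protocol does not say which.

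The in vitro study is the protocol's means of comparing RADTs with sampling error removed. The Existing research section says that a clinical validation study alone may not settle which RADT is best, and Phase II uses the best RADT from Phase 1. Justification of Support asks for laboratory technicians for one year for the in vitro studies and microbiology support, so the count also matters for planning workload and kits.

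**Working it through.** **Inputs** (all from the Protocol)

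- Group A strains: 4. Control strains: 1. Dilutions: "in three dilutions each". (In vitro section)
- Replicates: "We will perform 20 tests for each RADT at each dilution and for each strain", that is, 20 per cell. (In vitro section)
- Stated total: 200 per RADT. (In vitro section)
- RADTs: 5. Clinical precision target: +/-5 points at 95% confidence, sensitivity 85% to 95%. (Clinical study, Sample size)

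**Step 1. Try to reproduce 200.** Tests per RADT = strains x dilutions x 20.

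| Reading | Calculation | Tests per RADT |
|---|---|---|
| As written | 5 x 3 x 20 | 300 |
| Group A strains only | 4 x 3 x 20 | 240 |
| Group A at three dilutions, control at one | (4 x 3 + 1) x 20 | 260 |
| Five strains at two dilutions | 5 x 2 x 20 | 200 |

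Only the last row gives 200, and it contradicts the three dilutions. With three dilutions and 20 tests per cell, each strain uses 60 tests, and 200/60 = 3.33 is not a whole number of strains.

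**Step 2. Size of the discrepancy.** The described design has 240 group A tests and 1 x 3 x 20 = 60 control tests per RADT. Over five RADTs, 5 x 300 = 1,500 against 5 x 200 = 1,000, a gap of 500 tests, or 50% of the stated total. To keep 15 cells within 200 tests, replicates would be 200/15 = 13.3 per cell; 13 per cell gives 195 tests, of which 12 x 13 = 156 are on group A strains.

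**Step 3. Does the power statement survive?** The protocol does not define power here. I take it as the precision of sensitivity, because that is how the clinical study is sized.

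First, the clinical figures, n = 1.96^2 x p(1 - p)/0.05^2: p = 0.85 gives 195.9, p = 0.90 gives 138.3 and p = 0.95 gives 73.0. These reproduce the protocol's 196, 139 and 73.

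Then the in vitro 95% half-width, 1.96 x sqrt(p(1 - p)/n), pooled over group A strains and dilutions:

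| Group A tests | 85% | 90% | 95% |
|---|---|---|---|
| 240 (full design) | 4.5 | 3.8 | 2.8 |
| 160 (four fifths of 200) | 5.5 | 4.7 | 3.4 |
| 156 (13 per cell) | 5.6 | 4.7 | 3.4 |

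For example, 1.96 x sqrt(0.85 x 0.15/240) = 0.045. The clinical target is 5.0 points. The full design is better than this at every assumed sensitivity. The reduced one is about half a point worse at 85% and better at 90% and 95%.

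**The case against.** The best reply is that the operative instruction is 20 tests per dilution and strain, that a laboratory following it runs the full design, and that the bracketed 200 is a slip that understates the work. On that view nothing is lost but an accurate kit count. The effect on precision is indeed not adverse, no participants are involved, and no Phase II sample size depends on the figure. But 200 is the only total the section gives, it is the figure to which the power statement is attached, and nothing in the text tells the reader which of the two figures is the intended one.

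Two stronger readings are tempting, and the document supports neither.

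- A reader might infer that, because 200 is wrong, the claim of similar power is wrong too. It does not follow: pooled, both 240 and 160 group A tests give precision close to or better than the clinical study's.
- A reader might infer that the study is too imprecise because each dilution has only 4 x 20 = 80 group A tests, a half-width of 7.8 points at 85%. That sets one antigen load against a clinical figure pooled over all loads. It also assumes 85% at every dilution, although the section itself says that organism number crucially determines performance; at 95% the same 80 tests give 4.8 points. The protocol sets no per-dilution target. It describes the dilutions as covering the range of growths normally seen in the community, which fits a pooled comparison at least as well.

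**Conclusion.** The inconsistency is certain: the stated factors give 300 tests per RADT (240 group A, 60 control), not 200, and 1,500 rather than 1,000 over five RADTs. It affects the stated size and laboratory workload of one Phase 1 component. It does not show that the component is underpowered.

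The count rests on no assumption beyond the section's own numbers. The finding that similar power can stand rests on three: power means precision of sensitivity, results are pooled over strains and dilutions, and replicates are independent. The last is a simplification, since the 20 tests in a cell share one strain and one dilution, and the protocol gives no figure from which to allow for correlation.

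**What to change.** Make the factors and the total agree, in one of two ways:

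- Keep the described design and correct the total to 300 tests per RADT (240 group A, 60 control; 1,500 over five RADTs).
- If 200 is the real limit, restate the replicates as about 13 per cell (15 x 13 = 195 per RADT).

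In the same sentence, specify that similar power means the precision of sensitivity pooled over dilutions and strains: about +/-4.5 points at 85% with 240 group A tests, or about +/-5.5 with 160, treating replicates as independent, against +/-5 in the clinical study.

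The cost is one edited sentence. Keeping the design means 100 more tests per RADT (500 in all) than the stated total, if kits and technician time were planned on 200. Cutting the replicates needs no extra tests and costs about one point of pooled half-width at 85%.

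### The in vitro study's claim of power similar to the clinical study counts repeats on four group A strains as independent positives, and its stated total of 200 tests does not match its own design

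*Protocol*

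**What the plan says.** The protocol, under Phase 1, 3) In vitro study of RADTs, states the following:

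- Strains: "we will compare the performance of RADTs using 4 strains of group A" streptococci, "and a control strain (a group C streptococcus, or Moraxella".
- Loads: "in three dilutions each", at 10^5, 10^6 and 10^7 colony-forming units per ml.
- Repeats and total: "We will perform 20 tests for each RADT at each dilution and for each strain", with the total given in brackets directly after as 200 for each RADT.
- Power: "which will provide similar power to the clinical study".

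The clinical study it refers to is sized under Phase 1, 1) Clinical study of RADTs. That calculation assumes "a sensitivity of 85%-95% for the best RADT to estimate, with 95% confidence, sensitivity to within +/-5" percentage points, and concludes: "then 73 to 196 samples with streptococcus are required for each RADT".

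The protocol gives no within-strain correlation and no allowance for repeated tests on a strain. It does not say whether the 20 repeats come from one preparation or from fresh ones.

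**The concern.** The clinical requirement is a count of culture-positive samples. An adult gives at most four swabs, shared among five RADTs, so the positives for any one RADT can come from largely different patients. In vitro, every group A result comes from one of four strains. Setting the number of tests beside the number of clinical positives treats the 60 tests on a strain as 60 separate positives.

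The section on existing research warns that sampling error may stop the clinical study from settling which RADT is best, and offers the in vitro work as the way round this. The chosen RADT then goes into a Phase 2 trial arm. If in vitro precision is overstated, a difference between kits on four strains could be read as a firmer general result than it is. The stated total also disagrees with the design in the same sentence, so the size of the study is unclear.

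**Working it through.** **Inputs from the protocol.** 4 group A strains, 1 control strain, 3 dilutions, 20 tests per cell, stated total 200; clinical target ±5 points with 95% confidence at sensitivity 85–95%. The correlation ρ is not given and is assumed below.

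**1. Clinical benchmark.** n = 1.96² × p(1 − p) / 0.05².
- p = 0.85: 195.9, so 196
- p = 0.90: 138.3, so 139
- p = 0.95: 73.0, so 73

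The protocol's figures reproduce.

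**2. Number of in vitro tests per RADT.**
- Group A only: 4 × 3 × 20 = 240
- With the control strain: 5 × 3 × 20 = 300

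Neither equals 200.

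**3. Precision if all tests are independent.** Half-width = 1.96 × √(p(1 − p)/n), at p = 0.85:
- n = 200: 1.96 × √(0.1275/200) = 4.95 points
- n = 240: 4.5 points
- n = 80 (one dilution, 4 × 20): 7.8 points

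At one dilution the half-width is 6.6 points at 90% and 4.8 at 95%. The match to ±5 therefore needs pooling over dilutions as well as independence, except at 95% sensitivity.

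**4. Precision across strains, pooled over dilutions.** Effective n = 240 / (1 + (m − 1)ρ). If all of a strain's tests are correlated, m = 60. If correlation is confined to each strain-by-dilution cell, m = 20.

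| Assumed ρ | m = 60: design effect | Effective n | Half-width at 85% | m = 20: effective n | Half-width at 85% |
|---|---|---|---|---|---|
| 0 | 1.00 | 240 | 4.5 | 240 | 4.5 |
| 0.01 | 1.59 | 151 | 5.7 | 202 | 4.9 |
| 0.05 | 3.95 | 61 | 9.0 | 123 | 6.3 |
| 0.10 | 6.90 | 35 | 11.9 | 83 | 7.7 |

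The ρ at which 240 tests become worth fewer than n independent positives is (240/n − 1)/(m − 1). For n = 196, 139 and 73 this gives 0.004, 0.012 and 0.039 with m = 60, and 0.012, 0.038 and 0.120 with m = 20.

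These half-widths use 1.96. Between-strain variation estimated from four strains has 3 degrees of freedom (t = 3.18), so an interval built on it would be wider still.

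**5. Comparing kits on the same strains.** This was checked by simulating a detection-threshold model. All its parameters are assumptions: a probit curve in log10 load at 5, 6 and 7, mean threshold 5.4, slope SD 0.35, shared between-strain SD 0.2, and a second kit 0.2 log10 worse. Pooled sensitivity in this model is about 70%, so its half-widths should not be set against the 85% figures above.

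| Quantity | 4 strains × 20 repeats | 20 strains × 4 repeats |
|---|---|---|
| One kit's sensitivity, no interaction | ±6.8 | ±4.2 |
| Difference between kits, no interaction | ±4.4 | ±4.4 |
| Difference, RADT-by-strain SD 0.1 per kit | ±6.2 | ±4.8 |
| Difference, RADT-by-strain SD 0.2 per kit | ±9.9 | ±6.0 |

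**The case against.** The stated aim is comparative: kits are tested on a common panel at fixed loads so that sampling error is removed. For that purpose repeats are informative, and shared strain effects cancel, as step 5 shows. Following the strain number of the most recent in vitro study, and adding repeats because that study ran few tests per kit, is a reasoned choice. Breadth across natural isolates comes from the clinical study. A random-effects analysis by strain could be left to an analysis plan that is not shown. All of this stands, and it limits the point to the power statement, the total and the scope of the conclusions.

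A reader might go further than the protocol supports in three ways:

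- That all 20 repeats come from one suspension. Preparation is not described. Clustering by strain remains possible either way.
- That precision is much lower than claimed. This depends on a correlation the protocol does not give. With ρ = 0.01 confined to each cell, 202 of 240 tests remain effective.
- That four strains will rank the kits wrongly. This needs RADT-by-strain interaction, for which the protocol gives no evidence.

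What the objection does not rescue is the comparison of power, which the protocol makes without restricting it to kit differences or to the four strains.

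**Conclusion.** The point holds in a limited form. Two parts need no outside assumption: the stated 200 matches neither 240 nor 300, and one dilution falls short of ±5 points at 85% and 90% sensitivity (7.8 and 6.6) even with independent tests. The third part is conditional. For inference to group A streptococci in general, any positive within-strain correlation makes the 240 tests worth fewer independent positives. With correlation across a strain's 60 tests, a value of about 0.004 takes them below 196 and about 0.039 below 73. For ranking kits, the loss depends on RADT-by-strain interaction alone and may be nil.

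The four-strain design is not shown to be wrong, and the move to more strains is a preference. The point concerns Phase 1 only; the Phase 2 sample size is unaffected.

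**What to change.** 1. Reconcile the 200 with the strains, dilutions and repeats, and say whether the control strain is counted.
2. Withdraw the statement of similar power, or recompute it with an explicit allowance for clustering by strain, for each dilution, and for the difference between RADTs as well as for a single kit's sensitivity. State the assumed correlation and show a range.
3. Analyse with strain and RADT-by-strain terms. If four strains are kept, limit the conclusions to the tested panel.
4. State whether repeats are drawn from one preparation or from fresh ones.

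These changes cost drafting and analysis time only.

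Optionally, spread the same 240 group A tests over more strains, for example 20 strains × 3 dilutions × 4 repeats, keeping the four planned strains for comparability and adding isolates cultured in Phase 1. At the protocol's 25% positivity, 438 to 1176 patients would yield about 110 to 294 culture-positive patients. At ρ = 0.05 across a strain's 12 tests, effective n would be 240/1.55 = 155 instead of 61. No extra kits are needed. The cost is 20 × 3 = 60 strain-dilution combinations to prepare instead of 4 × 3 = 12, plus storage of isolates.
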